16.0 Data Management and Analysis

16.1 *Describe the data analysis plan, including any statistical procedures. This section applies to both quantitative and qualitative analysis.*

Response:

For two hypotheses, we first analyze a linear trend of dependent variables over time. If they are linear, we will use Generalized Estimating Equation to compare the two groups' slopes. A main effect and an interaction effect will be examined. If it is not, we will use Repeated Measures ANOVA with a between-factor. The contrasts within a group and the difference between groups will be performed as post hoc tests. To answer the last research question to find the difference between

the 4-months data and 6 month after intervention (or at 10 months), we will use Repaeated measurs ANVA with a between-factor.

To answer research questions, we will list all challenges for both groups and solutions for the treatment group. The effectiveness of solutions will be evaluated using a Likert Scale (from very effective to not effective at all) and percentages will be reported. For the rate of continued community, living at 4 months will be tabulated for both groups and a chi-square test will be used. The number of falls and emergency visits will be compared for these two groups using Mann Whitney U-test.

The significance level for primary analyses will be set at .05. SPSS 26.0 will be used for statistical analyses.

16.2 If applicable, provide a power analysis.

NOTE: This may not apply to certain types of studies, including chart/records reviews, survey studies, or observational studies. This question is asked to elicit whether the investigator has an adequate sample size to achieve the study objectives and justify a conclusion.

Response:

The sample size for this study was determined by a power analysis based on the study similar to our study (Kamiya et al., 2014). The effect size found in the article was $d = .65$. We will use a directional hypothesis; therefore, we set $\alpha = .05$, and in order to achieve 80% of statistical power, we will need 30 participants in each group, therefore 60 in total. Expecting 25% of attrition, we will recruit 75 participants.

16.3 Describe any procedures that will be used for quality control of collected data.

Response:

The data will be collected using a pen and paper and transferred to a computer software program (SPSS) file. The transferred data will be verified by an OTGS who is different from the data collector for missing data and correctness of data.

Confidentiality

A. Confidentiality of Study Data

Describe the local procedures for maintenance of confidentiality of study data and any records that will be reviewed for data collection.

*16.4 A. Where and how will all data and records be stored? Include information about: password protection, encryption, physical controls, authorization of access, and separation of identifiers and data, as applicable. Include physical (e.g. paper) **and** electronic files.*

Response:

Data in a paper form will be stored in a locked file cabinet in room [name] where only the PI can access with a key. This is separated from the identifiable information. Transferred data into SPSS will be stored in the UB Box, which is password protected and encrypted. Only study OTGS and PI can access the file with permission and a password.

The only link between personal identifiers such as name, address, phone number and data will be an ID number.

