1.0 Objectives

1.1 Describe the purpose, specific aims, or objectives of this research.

Response:

The purpose of this project is to develop and test affordable, effective strategies to reduce caregiver burden and associated negative effects (e.g., depression and fatigue) and to increase caregivers' satisfaction and self-efficacy, so that they can continue providing home-based care to their care recipients (CRs) who are members of the Program of All-inclusive Care for the Elderly (PACE). This project will connect PACE organizations and university occupational therapy (OT) graduate level curriculum to produce a practical, sustainable care model. In this project, a research component pertains to assess effectiveness of OT interventions

1.2 State the hypotheses to be tested, if applicable.

NOTE: A hypothesis is a specific, testable prediction about what you expect to happen in your study that corresponds with your above listed objectives.

Response:

We have three reteach questions and two hypotheses.

1. What are challenges that caregivers are facing in caring for their care recipients?
2. Which solutions were accepted and effective?
3. The intervention group will reduce caregiver burden and depression, while the control group will not.
4. The intervention group will increase the scores of positive aspect of caregiving and self-efficacy while the control group will not.
5. At 6-months after intervention, does the effect of our intervention exist?

In addition, we will identify the rate of care recipients who live in the community opposed to moving to a nursing home for both groups, and the number of falls and emerveny visits of care recipients.

Scientific Endpoints

2.1 Describe the scientific endpoint(s), the main result or occurrence under study.

*NOTE: Scientific endpoints are outcomes defined before the study begins to determine whether the objectives of the study have been met and to draw conclusions from the data. Include primary and secondary endpoints. Some example endpoints are: reduction of symptoms, improvement in quality of life, or survival. Your response should **not** be a date.*

Response:

Primary endpoint for the study is the reduction of caregiver burden and depression. Secondary endpoints is the improvement in positive aspect of caregiving and self-esteem.

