3.0 Study Design

3.1 Describe and explain the study design (e.g. case-control, cross-sectional, ethnographic, experimental, interventional, longitudinal, observational).

Response:

We will use a qualitative method to understand difficulties that caregivers are facing and to document solutions and their implementation process; and a quantitative method using a randomized contoured trial with pre-, post- and follow-up experimental design. A treatment group will receive a 1 to 2-month interventions to solve caregiving challenges, and a control group will receive usual support. Assessments will be conducted at baseline, 2 months (posttest), 4 months (follow-up), and 6 months post intervention.

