18.0 Withdrawal of Subjects

 N/A: This study is not enrolling subjects. This section does not apply.

18.1 Describe anticipated circumstances under which subjects may be withdrawn from the research without their consent.

Response:

We will not withdraw a participant from the research without their consent.

18.2 Describe any procedures for orderly termination.

NOTE: Examples may include return of study drug, exit interview with clinician. Include whether additional follow up is recommended for safety reasons for physical or emotional health.

Response:

If a participant decide to withdraw for the study, he/she will indicate it to an OTGS at the interview and the PI will confirm the wish through a phone contact with the participant.

18.3 Describe procedures that will be followed when subjects withdraw from the research, including retention of already collected data, and partial withdrawal from procedures with continued data collection, as applicable.

Response:

After the orderly termination, the data that had been collected until the withdrawal will be retained and analyzed. This information is included in the informed consent.

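### Section 16.1 lets an undefined linearity check on the outcomes choose between two tests that can disagree, and names no deciding effect or visit

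*Combined protocol and SAP*

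**What the plan says.** Section 16.1 starts with an analysis of the linear trend of the dependent variables and then splits. First branch: "If they are linear, we will use Generalized Estimating Equation to compare the two groups' slopes". Second branch: "If it is not, we will use Repeated Measures ANOVA with a between-factor". It continues "A main effect and an interaction effect will be examined" and "The contrasts within a group and the difference between groups will be performed as post hoc tests". The level for primary analyses is .05, with no sidedness given there.

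Section 16.2 sizes the trial at 30 per group from d = .65, 80% power and alpha .05, on the basis that "We will use a directional hypothesis".

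Hypothesis 3 in section 1.2 reads "The intervention group will reduce caregiver burden and depression, while the control group will not". It names no visit, and neither does the primary endpoint, which covers both burden and depression. Section 3.1 lists four measurement points: "Assessments will be conducted at baseline, 2 months (posttest), 4 months (follow-up), and 6 months post intervention". However, section 16.1 gives the comparison of 4 months with 10 months its own repeated measures ANOVA, so the natural visit set for the two hypotheses is 0, 2 and 4 months.

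**The concern.** Two analysts could follow section 16.1 faithfully on the same data and reach opposite conclusions on the primary endpoint. They would have to decide how to judge linearity, whether in both arms together or in one, and what to do if burden looks linear and depression does not. They would then have to decide whether the main effect or the interaction settles the hypothesis. Each choice would be made after the outcomes are in hand.

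The branches also answer different questions. One tests a difference in straight-line change; the other tests for any difference in pattern over the visits, without direction. The sample size was worked out for neither: it is the calculation for a single one-sided comparison of two means.

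**Working it through.** **1. The plan's own figure.** Normal approximation: n per group = 2(1.645 + 0.842)²/0.65² = 29.3, so 30. With the t distribution, 30 per group gives 80.0% power one-sided and 69.7% two-sided. The stated 30 reproduces, as a one-sided two-mean comparison.

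**2. Inputs for the comparison.** From the documents: visits 0/2/4; 75 recruited with 25% attrition, 75 × 0.75 = 56, so 28 per arm; effect 0.65 SD. Assumed, because the documents are silent: SD 1, equal correlation r = 0.6 between visits, no control-arm trend, two-sided 5%, and linearity judged by a t-test of y0 − 2·y2 + y4 at 5%, either pooled or in the treated arm only. Three effect shapes (months 0, 2, 4): halved (0, 0.65, 0.325), held (0, 0.65, 0.65) and linear (0, 0.325, 0.65).

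**3. What each branch tests.**
- GEE slope, complete data, exchangeable correlation: weights (t − 2)/8 = −0.25, 0, +0.25. This is month 4 minus baseline, divided by 4; the 2-month posttest gets no weight. SE of the difference in change = √(2(1 − 0.6) × 2/28) = 0.239. Halved: 0.325/0.239 = 1.36, power about 27%. Held or linear: 0.65/0.239 = 2.72, about 76%.
- ANOVA group-by-time F on 2 and 108 df: λ = (28/2) × Σ(δ − mean δ)²/(1 − 0.6). Halved and linear: 14 × 0.21125/0.4 = 7.39, about 67%. Held: 14 × 0.28167/0.4 = 9.86, about 80%.

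**4. Why the unstated arm rule matters.** For the halved shape the curvature in the treated arm is 0 − 1.3 + 0.325 = −0.975. Pooled over two equal arms it is half that, −0.4875, so the pooled check misses it more often and sends more trials to the weaker slope test.

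**5. Baseline-adjusted mean of months 2 and 4.** Residual variance = (1 + 0.6)/2 − 0.6² = 0.44; SE = √(0.44 × 2/28) = 0.177. Effects 0.4875, 0.65 and 0.4875 give ratios 2.75, 3.67 and 2.75, close to the simulated power below. Without baseline adjustment (change score) the variance is 0.8 + 1 − 1.2 = 0.6 and the SE 0.207, for 64/87/64%.

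**6. Simulation, 20,000 trials per case, r = 0.6.**

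| | Halved | Held | Linear |
|---|---|---|---|
| Branches disagree on significance | 43% | 13% | 13% |
| Power, current rule, pooled check | 50% | 77% | 76% |
| Power, current rule, treated-arm check | 67% | 82% | 76% |
| Power, baseline-adjusted mean of months 2 and 4 | 76% | 95% | 76% |

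**7. Type I error (r = 0.4 to 0.8).** Rule fixed, only the interaction decides: 5.0-5.3% (pooled check) or 5.9-6.1% (treated-arm check). Whichever branch is significant is reported: 7.4-7.9%. Either the group main effect or the interaction counts: 9.6-10.9%. Adjusted contrast: 5.1%.

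**8. Where the adjusted mean does worse than the current rule.** Effect only after month 2 (0, 0, 0.65), r = 0.6: 43% against 78-83%. Linear effect, r = 0.8: 93% against 96-97%. Halved effect under AR(1) correlation 0.8: 82% against 87-90%.

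**The case against.** Several stronger readings are tempting, and the documents do not support them.

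- *The plan has no between-group test.* It does: comparing the groups' slopes is a group-by-time interaction, and hypothesis 3 is about differential change. What is missing is a statement that this effect decides, given that a main effect is examined alongside it.
- *The trial runs at a 10% false-positive rate.* That needs success to be claimed on a main effect that averages in the baseline visit, which neither hypothesis states. The 7-8% figure needs the branch to be chosen by its p-value, which breaks the plan's own rule. The text excludes neither, but it prescribes neither.
- *The slope runs over all four assessments, so an early gain counts against the treatment.* Section 3.1 alone could suggest this. Section 16.1 analyses month 10 separately, and section 17.5 describes three collections in 4 months, so the three-visit reading is the better one.
- *Repeated measures ANOVA will discard caregivers with a missing visit, contrary to section 18.3.* That is how the procedure is usually run, but the plan does not say so. Section 18.3 says "the data that had been collected until the withdrawal will be retained and analyzed"; it does not require every analysis to include everyone.
- *A single model is always more powerful.* Steps 5 and 8 show otherwise: most of the gain comes from baseline adjustment, a separate merit, and it reverses under some effect shapes and correlations.

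What survives all of this is that the linearity rule is undefined, that no deciding effect or visit is named, and that the branches can disagree.

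**Conclusion.** The point holds and should be fixed. That the rule is undefined and the deciding test unnamed is plain from the text and needs no simulation. The practical size depends on how the effect evolves: disagreement between branches is substantial if the effect fades after the posttest and modest if it is held or grows steadily. A rule fixed in advance, with the interaction deciding, does little harm to type I error; the exposure lies in what is left unwritten. Confidence in the power comparison is only moderate, because the correlation, effect shapes and form of the linearity check are all assumptions.

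**What to change.** Replace the two-branch rule in section 16.1 with one pre-specified linear mixed model per outcome (SPSS MIXED) on the 2- and 4-month scores. Include group, visit as a category, group by visit and the baseline score, with a stated covariance structure, and analyse as randomised using all observed visits. Baseline may enter as a covariate, or as an outcome with a common baseline mean. The second version also keeps caregivers who have only a baseline score, which fits section 18.3 best.

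Before outcomes are examined, state:
- the one between-group contrast that decides: a single visit, or the mean of months 2 and 4;
- whether the test is one- or two-sided, in line with section 16.2;
- how burden and depression are combined, since a model per outcome still leaves two primary tests at .05.

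The choice of contrast should follow the expected course of the effect. The averaged contrast suits an effect expected by the posttest. At r = 0.6 the adjusted 2-month score alone has 84% power if the effect fades but 32% if it builds linearly. The averaged contrast carries the losses in step 8, above all for an effect that appears only after the posttest.

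The cost is about one paragraph of wording; visits, data and software stay the same.

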addressing the medical needs of the care recipient rather than the caregiver. Another finding from previous research is that interventions that are individually customized to the care recipient and caregiver's needs are more effective than generalized interventions (Pinquart & Sørensen, 2006). There are interventions and educational programs for caregivers that have shown to be effective (Austrom & Lu, 2009). Support groups are effective to help caregivers, but currently no program supports caregivers by instructing how to provide care for care recipient's ADLs, which is the core of caregiving tasks. Occupational therapist (OT) can apply their knowledge in providing care for patients with dementia to caregivers. In doing so, we realize that practical solutions for the challenges that caregivers are facing can be developed using a caregiver-centered approach, rather than a top-down approach. Therefore, individualized interventions for the caregiver determined on a case-by-case basis by a team of gerontologists, occupational therapists, and occupational therapy students, which can be finalized by the input from caregivers, may lead to a better outcome for caregiving situations. In addition we explore if positive effects of caregiver support will last six months after the intervention because it will find if continuous support is needed for this target population. Currently, related studies do not exist.

2.2 Include complete citations or references.

2.3

Response:

Austrom M G, & Lu, Y. (2009). Long term caregiving: helping families of persons with mild cognitive impairment cope. *Current Alzheimer Research*, 6 (4), 392-398.

Dean K & Wilcock G. (2012) living with mild cognitive impairment: the patient's and carer's experience. *International Psychogeriatrics*, 24(6), 871-881.

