A month after initial assessment, OTGS will contact CRs for follow-up and 2 months later, the posttest will be administered. At 4 months, follow-up interview will occur. The number of home visits (4-6) will vary depending on case. Finally 6 months after the intervention, a phone call will be made, asking the same questions before and the number of falls and emergency visits of care recipients in the past 10 months. After each interview, a participant will be paid \$20. (The total maximum is \$80).

9.2 Describe what data will be collected.

NOTE: For studies with multiple data collection points or long-term follow up, consider the addition of a schedule or table in your response.

Response:

The outcome measures will use established instruments. To measure caregiver burden, 12-item Zarit Burden Interview (ZBI), for depression, 20-item Center for Epidemiology Study-Depression (CES-D) will be used. Positive Aspect of Caregiving has 9 items. Self-esteem and fatigue questions will use a visual analog scale from 1 to 10. In addition, items of activities of daily living (ADL, e.g., eating, dressing, and toileting) and instrumental ADL (IADL, e.g., meal preparation, housekeeping) that caregivers are assisting will be identified. We do not assess or provide interventions for CRs directly, but we ask caregivers about CR's cognitive levels using Global Deterioration Scale, and functional levels using FIM to assess ADL and OARS' IADL. We also ask if care recipients fell or visited an emergency room.

 *9.3 List any instruments or measurement tools used to collect data (e.g. questionnaire, interview guide, validated instrument, data collection form).*

Include copies of these documents with your submission.

Response:

The assessment form is attached.

9.4 Describe any source records that will be used to collect data about subjects (e.g. school records, electronic medical records).

Response:

We will not use other sources or records. But if the cause of cognitive impairment is not clear, we will ask the PACE to provide it for us. This is written in the consent form.

*9.5 Indicate whether or not **individual** subject results, such as results of investigational diagnostic tests, genetic tests, or incidental findings will be shared with subjects or others (e.g., the subject's primary care physician) and if so, describe how these will be shared.*

Response:

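### Question 5 asks whether the effect exists six months after the intervention, but its named analysis compares 4-month with final scores and does not specify the group difference at the final assessment

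*Combined protocol and SAP*

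**What the plan says.** Section 1.2 (Objectives), item 5, asks: "At 6-months after intervention, does the effect of our intervention exist". Section 2.1 (Background) gives the reason: "we explore if positive effects of caregiver support will last six months after the intervention because it will find if continuous support is needed". The data are collected. Section 9.1 (Procedures) states: "Finally 6 months after the intervention, a phone call will be made, asking the same questions before", and does not restrict that call to one arm.

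Section 16.1 (data analysis plan) begins its answer with "To answer the last research question to find the difference between" and continues: "the 4-months data and 6 month after intervention (or at 10 months), we will use Repaeated measurs ANVA with a between-factor". It names no treatment-versus-control contrast at the final assessment.

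Two other statements in Section 16.1 bear on this, both in the text on the two hypotheses:
- On the main model: "If they are linear, we will use Generalized Estimating Equation to compare the two groups", where the comparison is of slopes.
- On follow-up tests: "The contrasts within a group and the difference between groups will be performed as post hoc tests", with no visit named.

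**The concern.** Whether an effect exists at a given time is a question about the difference between arms at that time. Whether scores moved between two visits is a different question. The plan poses the first and names an analysis built for the second.

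Section 2.1 says the answer will show whether caregivers need continuing support. Two misreadings are possible:
- A non-significant interaction could be reported as a lasting effect although there was no effect to last.
- A significant group term could be reported as a lasting effect although the 4-month scores alone produced it.

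The question is exploratory, and hypotheses 3 and 4 do not depend on it.

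**Working it through.** **1. What each ANOVA term tests.** Let D4 and DF be the true group differences at 4 months and at the final assessment.
- Time: the change averaged over both arms. It does not compare the arms.
- Group-by-time: DF − D4. It is zero when the effect fully persists (0.65 − 0.65) and when there was none (0 − 0).
- Group: (D4 + DF)/2. It separates those two cases, but it equals 0.325 when D4 = 0.65 and DF = 0.

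None of these is DF.

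**2. The plan's own figure.** Sections 4.3 and 16.2 give d = 0.65, directional α = .05, 80% power and 30 per group. The normal formula gives 2(1.645 + 0.842)²/0.65² = 29.3, so 30; the t-based power at 30 is 80.0%. The figure reproduces. It describes a single comparison of two groups. A direct unadjusted final-visit test with 30 per group has 80.0% power one-sided, or 69.7% two-sided, if d = 0.65 persists.

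**3. Inputs for the size of the problem.** The sample is 75 recruited less 25% attrition: 75 × 0.75 / 2 = 28.1, taken as 28 per arm. D4 = 0.65 is taken from the power analysis. Assumed, because the documents do not give them: SD 1 at each visit, and correlation ρ of 0.5, 0.6 or 0.7 (4-month to final for the ANOVA terms, baseline to final for ANCOVA). Tests are two-sided at .05 using the noncentral t, with noncentrality equal to the standardized effect × √(28/2).

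**4. Formulas for the standardized effect.**
- Group term: [(D4 + DF)/2] / √((1 + ρ)/2), df 54
- Interaction: (D4 − DF) / √(2(1 − ρ)), df 54
- Final-visit ANCOVA: DF / √(1 − ρ²), df 53

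Example at ρ = 0.5 with nothing left: the group term is 0.325/√0.75 = 0.375, noncentrality 0.375 × √14 = 1.40, and the probability of significance is 0.281.

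| Probability of a significant result | ρ = 0.5 | ρ = 0.6 | ρ = 0.7 |
|---|---|---|---|
| Group term, effect fully persists | 0.788 | 0.761 | 0.736 |
| Group term, half remains | 0.543 | 0.517 | 0.493 |
| Group term, none remains | 0.281 | 0.267 | 0.254 |
| Interaction, total loss | 0.666 | 0.761 | 0.869 |
| Interaction, half lost | 0.223 | 0.267 | 0.338 |
| Final-visit ANCOVA, effect fully persists | 0.787 | 0.847 | 0.917 |
| Final-visit ANCOVA, half remains | 0.281 | 0.320 | 0.387 |

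When no effect remains, the final-visit test rejects 5% of the time by construction. If there never was an effect, the group term also rejects 5% of the time.

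**5. Precision of the final-visit difference.** The 95% half-width is t × √(1 − ρ²) × √(2/28). At ρ = 0.5 this is 2.006 × 0.866 × 0.267 = 0.464 SD. It is 0.429 at ρ = 0.6 and 0.383 at ρ = 0.7.

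**6. Sensitivity.**
- ρ = 0.3: ANCOVA power 0.706 (full) and 0.240 (half), half-width 0.511 SD.
- No baseline adjustment: power 0.666 (full) and 0.223 (half).
- One-sided .05: the group term is significant 0.398/0.381/0.366 of the time with none left; ANCOVA power is 0.870/0.912/0.957 (full) and 0.398/0.443/0.514 (half).

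**7. Simulation check.** With 30 per arm, ρ from 0.3 to 0.8 and 20,000 runs per scenario, the interaction rejected about 5% of the time both under full persistence and under no effect ever. With the effect lost by the final visit, the group term rejected 26.5% to 33.8% of the time, and the direct final-visit test about 5%.

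**The case against.** The strongest reply is that nobody would read the group term alone. The same ANOVA yields the interaction, which detects total loss 67–87% of the time. Counting only results where the group term favours treatment and the interaction is not significant, a wrong conclusion of persistence after total loss occurs about 9%, 6% and 3% of the time at ρ = 0.5, 0.6 and 0.7, and about 15% at ρ = 0.3. That stands as arithmetic, and it means 25–28% overstates the risk for an analyst who reads both terms. But the plan sets no such rule for question 5. The pair still does not estimate the final difference, and with half the effect lost the interaction notices only 22–34% of the time.

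It can also be said that Section 2.1 asks whether effects last, which a comparison of 4-month with final scores by group does address once an effect has been shown. That is fair for maintenance. Item 5 of Section 1.2, however, asks whether the effect exists.

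The post hoc sentence could be stretched to cover question 5, and the planned ANOVA could produce the contrast. Likewise, if the final visit enters the main model and the linear branch holds, a fitted final difference could be derived from it. The plan says none of this. The gap is therefore in what is specified, not in what the models can do.

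**Conclusion.** The concern holds and should be fixed. The analysis named for question 5 does not commit to the estimate that answers it, and either ANOVA term taken alone can mislead. The logical mismatch needs no assumptions. The size does: 28 per arm, d = 0.65 at 4 months, equal SDs and an assumed correlation. On that basis the group term is significant 25–28% of the time when nothing remains (37–40% one-sided, the direction the power analysis states), and the interaction cannot tell full persistence from no effect at any correlation. The consequence is limited to an exploratory question, though one the protocol uses to judge whether support must continue.

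**What to change.** In Section 16.1, name the between-group difference at the final assessment, adjusted for baseline and with a 95% confidence interval, as the answer to question 5. Take it from an ANCOVA at that visit or from a longitudinal model with visit as a categorical factor. The planned comparison of GEE slopes is not itself this difference. Naming an unadjusted final-visit contrast within the planned ANOVA would also close the gap, with lower power (67% against 79–92% if the full effect persists).

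Report the change in the group difference from 4 months to the final assessment, with its interval, as descriptive. State in advance that a non-significant final difference is not evidence of no effect.

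The cost is one extra model and a short edit, with no new visits or data. The drawback is that two-sided power is only 28–39% if half the effect remains, with an interval half-width of about 0.38 to 0.46 SD. The conclusion must therefore rest on the interval rather than on the p-value.

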9.0 Procedures Involved

9.1 Provide a description of **all research procedures or activities being performed and when they are performed once a subject is screened and determined to be eligible. Provide as much detail as possible.**

NOTE: This should serve as a blueprint for your study and include enough detail so that another investigator could pick up your protocol and replicate the research. For studies that have multiple or complex visits or procedures, consider the addition of a schedule of events table in in your response.

Response:

After obtaining approval from the IRB, UB OT graduate students (OTGS) will be educated and trained for 2 months prior to the start of the intervention. They will study the protocol, interview methods, and interventions. PACE rehabilitation, department staff will also be educated

about the protocol and they will mail an invitation letter and a flyer to caregivers of person with dementia. These records are readily available at the PACE as a standard record keeping procedure.

Interested caregivers will contact the PI and will be screened for eligibility for the study.

OTGS will make an appointment to visit participants. While reading a consent form, an OTGS will explain the study in detail and make sure that the caregiver understand the content. Their right to withdraw from the study without penalty will be explained. After obtaining written consent, a structured interview will take place about 30 minutes. It starts with asking demographic questions, care recipient's cognitive and physical function, levels of assistance the caregiver is providing, and followed by questions about caregivers. This section will ask caregiver burden, fatigue, depression, positive aspect of caregiving, and self-efficacy in caregiving.

The OTGS will talk with caregivers to understand problems in depth. Examples may include difficulty in (a) understanding the disease development process and its consequences; (b) assisting care recipient (CR)'s ADL, IADL, and communication; (c) coping with CRs' undesirable behaviors (e.g., non-use of a stair glide, pulling a cord to turn off lights, reluctance in changing clothes and washing hair, inactivity and lack of motivation in daily routine); (d) maintaining caregivers' health and strength; (e) coordination of care among family members, and (f) having own time. In addition, we will specifically address fall prevention because PACE enrollees have a high fall rate.

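### Question 5 needs a group difference at month 10, but its model leaves out the baseline score; adding it, mean-centred, would sharpen that estimate at almost no cost

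*Combined protocol and SAP*

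**What the plan says.** The fifth item in Section 1.2 asks: "At 6-months after intervention, does the effect of our intervention exist". Section 16.1 gives this item its own analysis. It begins "To answer the last research question to find the difference between" and continues "the 4-months data and 6 month after intervention (or at 10 months), we will use Repaeated measurs ANVA with a between-factor". Two visits and one between-subject factor are named. No covariate is named here or for any other model, and the section does not say which term of the ANOVA (group, time or group-by-time) answers the question.

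The baseline scores exist. Section 3.1 states: "Assessments will be conducted at baseline, 2 months (posttest), 4 months (follow-up), and 6 months post intervention". Section 9.1 describes the first interview: "This section will ask caregiver burden, fatigue, depression, positive aspect of caregiving, and self-efficacy in caregiving".

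The two main hypotheses are handled differently. Their outcomes are modelled over time: "If they are linear, we will use Generalized Estimating Equation to compare the two groups' slopes", with repeated measures ANOVA as the alternative. There, baseline can enter as one of the visits.

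**The concern.** Whether an effect exists at month 10 can only be answered by comparing the groups at month 10. The change in the group gap between months 4 and 10 cannot settle it: no change is compatible both with an effect that lasted and with an effect that was never there. The answer therefore has to come from a group difference, and in the model as specified that is a raw comparison of follow-up scores.

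Two things follow. With about 30 caregivers per arm, part of any chance difference in starting burden or depression score carries through to month 10, where it can look like a lasting effect or mask one. And variance between caregivers that the baseline score would explain stays in the error term. If adjustment is not specified in advance, there is also room to choose between adjusted and unadjusted results once an imbalance has been seen.

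**Working it through.** **Inputs.** From Sections 4.3 and 16.2: d = 0.65, directional test at .05, 80% power, 30 per group, 75 recruited with 25% attrition. Not in the documents: the correlation rho between visits. I assume it equal for all pairs of visits, with equal SDs, and take 0.3, 0.5 and 0.7. The documents give no effect size for month 10, so d = 0.65 is carried over from the general power statement.

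**1. The plan's own figure.** A one-sided two-sample t-test with d = 0.65, alpha .05 and 80% power needs 29.97 per group, so 30. Power at 30 is 80.0%. The stated size reproduces.

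**2. Month-10 group difference.** In SD² units the variance of a score is 1 unadjusted and 1 − rho² after adjustment for baseline. The standardised effect becomes 0.65/√(1 − rho²), and the error df go from 58 to 57. At rho = 0.5: 1 − 0.25 = 0.75, and 0.65/√0.75 = 0.751.

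| rho | variance cut | SE cut | one-sided power (unadjusted 80.0%) | two-sided power (unadjusted 69.7%) |
|---|---|---|---|---|
| 0.3 | 9% | 5% | 83.2% | 73.7% |
| 0.5 | 25% | 13% | 89.0% | 81.5% |
| 0.7 | 49% | 29% | 96.7% | 93.4% |

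The planned attrition leaves 75 × 0.75 = 56.25, about 28 per arm. At rho = 0.5, month-10 power there goes from 77.5% to 87.0% one-sided, or from 66.6% to 78.7% two-sided.

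**3. Group term averaged over months 4 and 10.** The variance goes from (1 + rho)/2 to (1 + rho)/2 − rho². At rho = 0.5 this is 0.75 to 0.50, a cut of 33% (14% at rho 0.3, 58% at rho 0.7).

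**4. Group-by-time term (change from month 4 to month 10).** The variance is 2(1 − rho) with or without baseline when baseline correlates equally with both visits. In four cases with unequal correlations the cut was about 1% to 7%.

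**5. Chance imbalance.** The SD of the baseline difference between arms is √(2/30) = 0.258 SD. A gap above 0.3 SD in either direction has probability 0.245. At rho = 0.5, a 0.3 SD gap shifts the unadjusted month-10 difference by 0.5 × 0.3 = 0.15 SD, and 0.15/0.65 = 23% of the planned effect.

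**6. Simulation check.** In 20,000 trials with 30 per arm and rho = 0.5, each 1 SD of baseline gap moved the month-10 difference by 0.50 SD and the month-4-to-10 contrast by about 0.00 SD. Adjustment cut the variance of the month-10 difference by 23.7%, slightly below the formula's 25% because the slope has to be estimated. The variance of the group-by-time contrast did not fall (0.0667 before, 0.0684 after).

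**7. Centring.** In a repeated measures ANOVA with an uncentred covariate, the test of time refers to a caregiver whose baseline score is zero. I simulated 30 per arm, rho = 0.5, a baseline mean 2.5 SD above zero and a true change of 0.4 SD from month 4 to month 10 (all assumed), tested two-sided. Power of the time test was about 86% with no covariate, about 20% with an uncentred covariate and about 86% with a centred one.

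**The case against.** The strongest case is that Section 16.1 states its own target, the difference between the 4-month and the 10-month data. Read as change over time, that term does not suffer: baseline imbalance cancels and adjustment gains nothing under equal correlations. This stands for that term. It does not remove the point, because Section 1.2 asks whether the effect exists, and that term cannot say.

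Second, a reader might infer that leaving out baseline biases the durability result. The documents do not support this. The trial is randomised, so the unadjusted comparison is unbiased, and chance imbalance is already reflected in its standard error and error rate. What is lost is precision, and protection in the individual trial from an imbalance that can be seen.

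Third, a reader might put the loss at a quarter to a third of the precision. That is a variance cut at rho = 0.5 only. Over 0.3 to 0.7 the cut runs from 9% to 58% across the two group contrasts, and at 0.5 the standard error falls by only 13% to 18%. At rho = 0.3 the gain in month-10 power is 3 to 4 points.

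Fourth, on the plan's directional basis, unadjusted power at 30 per arm already reaches 80%. That is correct, given that d = 0.65 still applies at month 10 and 30 per arm remain.

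Fifth, the plan is silent on baseline rather than excluding it, and the main models do not list their visits, so month 10 might also appear there. That stands too, and it is why this should not be called the only analysis of durability. But a two-visit ANOVA contains no third score unless one is added.

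**Conclusion.** The point holds as a nearly free improvement, not as an error that invalidates the analysis. The question in Section 1.2 needs a group difference at month 10. The model in Section 16.1 would give it without the baseline score that every caregiver provides. The size depends on a correlation that the plan does not state: small at 0.3, worth having at 0.5 (about 9 points of power one-sided, about 12 two-sided) and large at 0.7. These figures rest on equal correlations and SDs, d = 0.65 at month 10 and 30 per arm. No gain should be claimed for the month-4-to-10 group-by-time term. Which term answers question 5 has to be settled together with the covariate, because the benefit depends on it.

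**What to change.** In Section 16.1, for question 5, state that:

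- the answer is the between-group difference at month 10 (6 months after intervention), not an average with month 4;
- it is estimated with the baseline score of the same outcome as a covariate, centred at its mean, either by ANCOVA at month 10 or by the two-visit model with a group-by-visit term and centred baseline;
- the comparison of change from month 4 to month 10 is kept as a supporting result.

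Centring must be written in; otherwise the test of time in the two-visit model is distorted. The cost is about one sentence and one degree of freedom in the month-10 comparison. No new data or staff are needed.
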